- Eye Diseases which limit the ability of light to be processed (e.g., untreated cataracts, severe glaucoma, macular degeneration, blindness, pupil dilation problems or retina damage)
- Secondary cancer diagnosis within the last 5 years
- Severe sleep disorders (e.g., Narcolepsy)
- History of bipolar disorder or manic episodes (which is a contra-indication for light treatment)
- Severe psychological impairment (e.g., hospitalization for depressive episode in the past 12 months)
- Previous use of light therapy to alleviate fatigue or depressive symptoms

c) Number of Subjects

 Mount Sinai	Protocol Name:	Systematic Programmed Illumination of Hospital Rooms to Prevent/Reduce Cancer-Related Fatigue during Autologous Stem Cell Transplantation for Multiple Myeloma
	Principal Investigator:	[name]; [contact]
	Primary Contact Name/Contact Info:	[name], [contact], [contact]
	Date Revised:	8/15/2019
	Study Number:	IF# 2517160 HS# 15-00777 GCO#: 15-2009

For this feasibility study, we will recruit 60 participants drawn from the pool of upcoming HSCT admissions to treat MM at the MSH bone marrow transplant (BMT) clinic. Our previous research has demonstrated that at least 40% of this group either suffers from or will develop clinically significant fatigue related to cancer or its treatment.

d) Study Timelines

Total participation in this study is 16-18 weeks, and may vary by hospital admission, length of hospital stay, and expediency of returning study related materials.

Endpoints

The primary endpoints in the proposed study are: 1) Fatigue as measured by a simple Graphic Rating Scale, Multidimensional Fatigue FACIT Fatigue Scale, and The Pittsburgh Sleep Quality Index; 3) Depression as measured by the CES-D; 4) Quality of Life measured by the SF-36 scale; 5) Sleep/wake activity measured using an actigraph; and 7) Biological variables melatonin and inflammatory markers (i.e., IL-1ra, IL-6, MCP-1/CCL2, MIP-1a/CCL3, sTNFr1, sIL-6R, CRP) as obtained via urine and blood analysis.

The secondary endpoints include: 1) the amount of light received by the patient as measured by the Daysimeter; 2) treatment satisfaction using the FACIT-TS-G scale, and 3) Psychological moderators (e.g., emotions, symptom burden) that may affect for whom the treatment is effective.

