Data from any web-based assessment tools will be accessible to research study team using password protection and will only be identified by participant ID number. Paper files and printouts of assessment scores will be kept in a locked cabinet with access only by authorized project research staff. The use of email will be in accordance with MSH policy (i.e. secure email, obtaining consent from subject to send email, etc.).

Urine and blood samples will be marked only by study ID number and no other identifying information.

Data Analysis:

Descriptive statistics will be calculated both for the entire group and separately for each treatment group. T-tests and Fisher's exact tests will be used to assess group differences at baseline for possible confounders (i.e., demographic variables, clinical characteristics, and medications). Any variables showing differences between the two groups will be used as covariates in subsequent analyses. Since there is no known seasonality effect to measures of fatigue or to measures of sleep, which are our main outcome measures, seasonality will not be controlled in these analyses. For the primary outcome (Fatigue), the secondary outcomes (Depression, Sleep, Circadian Activity Rhythms, melatonin (exploratory), and Quality

	Protocol Name:	Systematic Programmed Illumination of Hospital Rooms to Prevent/Reduce Cancer-Related Fatigue during Autologous Stem Cell Transplantation for Multiple Myeloma
	Principal Investigator:	[name]; [contact]
	Primary Contact Name/Contact Info:	[name], [contact], [contact]
	Date Revised:	8/15/2019
	Study Number:	IF# 2517160 HS# 15-00777 GCO#: 15-2009

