of Life), hierarchical random effects linear mixed models will be employed for Aims 1 and 2 using MIXED with repeated measures. Besides time (linear and possibly quadratic trends to allow for possible nonlinear trends), any covariates identified in the preliminary analyses and intervention group will be assessed in a fixed effects model. Each model will also include a random intercept. Post-hoc comparisons will be Tukey-adjusted. Since there are multiple secondary outcomes, the p-values will be Sidak adjusted for correlated multiple comparisons. Any variations in length of hospital stay (i.e., length of intervention) will be used as a covariate in all analyses. This is highly unexpected since 90% of ASCT patients are hospitalized for 14 days. In the Analysis of Aim 2, we will establish that the treatment is a significant predictor of the primary outcome (CRF) as well as the hypothesized mediators. Next, we will first examine the role of each of the mediators of the effects of sPI on CRF by introducing each individually into the equation which contains the time variable, the treatment main effect, and the time by treatment interaction. Each mediator which is a significant predictor of CRF in this equation will then be combined with any other significant mediating predictor of CRF into a single equation. We predict the introduction of each significant mediator will result in the decrease in the significance of the time by treatment interaction effect on CRF. However, the more important test of the mediating role by any variable will depend on the statistical significance of the indirect path from treatment to mediator and from mediator to the outcome. Following procedures suggested by Shrout and Bolger (2002), 1000 bootstrap samples will be employed to determine the significance of each indirect path.⁵⁰ **Power:** It is difficult to discuss power for **Aim 1** and **Aim 2** since there is no directly relevant past research. As a consequence, one of the goals of this project is to obtain estimates of the effect sizes that will eventuate from our proposed analyses. Although unknown at the moment, these effect sizes can guide decisions regarding sample sizes for a larger scale grant. In the interim, there are three lines of research that may provide some guidance. The first involves the work of [name], who investigated the effects of light treatment on fatigue experienced by women undergoing chemotherapy for breast cancer.⁹ Using her results, we calculated power for a repeated measures design with an autoregressive lag 1 structure and autocorrelations ranging from 0.40 to 0.60. With alpha equal to 0.05 and a sample size of 30 patients per group, power ranged between 0.96 and 0.98. We followed a similar approach using [name]'s results but focusing only on MM survivors of ASCT.¹⁰ In this case, power was 0.99 for autocorrelations ranging between 0.40 and 0.60. However, the latter results must be treated cautiously because these calculations were based on a very small sample (N = 17 survivors). Using the same small sample, our repeated measures analysis of depression indicated that the time by treatment condition interaction was marginally significant (p = 0.0568). The F-ratio for this interaction yielded an eta coefficient of 0.48 which would be considered moderately strong following Cohen's criteria.⁴⁹ We hypothesize that the interaction effect would have been significant had the sample size been larger as is being proposed in this study (N = 60). Because of the very small survivors sample and the variability of our indicator of circadian activity rhythms (the f-statistic), the Mixed program did not converge and it was not possible to obtain a power estimate for this outcome. The third line of research that is germane to power in the proposed pilot study was conducted by Sim and Lewis who applied the UCL approach and found that a pilot sample of n => 55 would minimize the overall sample size for small to medium standardized effect sizes (0.2-0.6).

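### Section 5d and Data Analysis contradict each other on which outcomes are primary, FACIT-Fatigue is not carried from Hypothesis 1a into either, and the Aim 1 model names no group-by-time term or contrast.

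*Combined protocol and SAP*

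**What the plan says.** **Section 5d, Endpoints.** The list begins "The primary endpoints in the proposed study are: 1) Fatigue as measured by a simple Graphic Rating Scale, Multidimensional Fatigue FACIT Fatigue Scale". It continues with PSQI, CES-D, SF-36, actigraphy, melatonin and seven named inflammatory markers, all called primary. Its secondary list is light received, treatment satisfaction and psychological moderators.

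**Data Analysis (section 5g).** The outcomes are introduced as "For the primary outcome (Fatigue), the secondary outcomes (Depression, Sleep, Circadian Activity Rhythms, melatonin (exploratory), and Quality" of life. Fatigue is the only primary outcome and no scale is named. Inflammatory markers are not listed. Just before this, the seasonality remark refers to "measures of fatigue or to measures of sleep, which are our main outcome measures". The multiplicity rule is: "Since there are multiple secondary outcomes, the p-values will be Sidak adjusted for correlated multiple comparisons".

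**Aim 1 model.** Besides linear and possibly quadratic time, "any covariates identified in the preliminary analyses and intervention group will be assessed in a fixed effects model", with a random intercept. Time-by-treatment appears in the Aim 2 text, where mediators are added to "the equation which contains the time variable, the treatment main effect, and the time by treatment interaction", and in the Power paragraph, where "our repeated measures analysis of depression indicated that the time by treatment condition interaction was marginally significant".

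**Scale.** Hypothesis 1a attaches FACIT-Fatigue to cancer-related fatigue. The measures list in section 5e calls it an outcome measure of fatigue, and has the line scale take its place for daily ratings in hospital.

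**The concern.** The two sections give opposite labels to CES-D, SF-36, PSQI and actigraphy. No damage to a table or gap in the text could produce that. The label matters because the only multiplicity rule across outcomes applies to secondary outcomes. Anyone who takes the labels from section 5d would have no adjustment rule for most of the efficacy outcomes.

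The second problem is what Aim 1 estimates. Hypothesis 1a concerns the hospital stay. The listed fixed effects give one group difference averaged over every assessment, including the baseline before any light was delivered and the visits up to three months after discharge. No time point or contrast is named.

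Two uses of the result depend on this. Aim 1 asks whether the intervention has a significant effect, and the Power paragraph says the effect sizes obtained should guide the sample size of a larger study. If the scale, term and time point stay open, that effect size can be chosen after the data are seen. Feasibility under Aim 3 does not depend on it.

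**Working it through.** **The plan's own figure.** The Power paragraph states "With alpha equal to 0.05 and a sample size of 30 patients per group, power ranged between 0.96 and 0.98". It cannot be reproduced, because the effect size, standard deviation, number of time points, scale and tested term are not given. It can only be back-solved. For a single time point, 30 per arm and two-sided 0.05 (the documents do not state sidedness), d = (1.960 + z_power)/√15. This gives 3.711/3.873 = 0.96 for power 0.96 and 4.014/3.873 = 1.04 for power 0.98. The figure is neither confirmed nor refuted, and it does not show which scale or term was meant.

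**The two sections side by side.**

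| Outcome | Section 5d | Data Analysis |
|---|---|---|
| Fatigue | primary, several scales | primary, no scale named |
| Sleep (PSQI, actigraphy) | primary | secondary, Sidak (also called a main outcome) |
| Depression (CES-D) | primary | secondary, Sidak |
| Quality of life (SF-36) | primary | secondary, Sidak |
| Circadian activity rhythms | not listed separately; actigraphy is primary | secondary, Sidak |
| Melatonin | primary | listed with the secondary outcomes, marked exploratory |
| Inflammatory markers (7) | primary | not in the outcome list |

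**What the tested term would estimate.** This is an illustration. The assessments follow the schedule in section 5e, Methods: baseline, day of transplant, day +2, day +7, engraftment day 3, one month and three months after discharge, which is seven. Three things are assumed: FACIT-Fatigue is given at each, the data are complete, and the benefit follows one of two patterns.

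- Hospital-only: 0, 0, 0.5d, d, d, 0, 0. Section 8 allows for this, since it says fatigue may return once the light stops.
- Persisting: 0, 0, 0.5d, d, d, d, d.

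*Group main effect.* With a random intercept and balanced data, this is the mean of the seven differences.

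- Hospital-only: 2.5d/7 = 0.36d.
- Persisting: 4.5d/7 = 0.64d.
- With baseline left out: 2.5d/6 = 0.42d and 4.5d/6 = 0.75d. Baseline therefore explains part of the dilution. The rest comes from the assumed slow onset and, in the first pattern, from the two follow-up visits.

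*Change from baseline at engraftment day 3.* This is d under both patterns.

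*Linear group-by-time, first to last assessment.* This is Σ(t − t̄)y / Σ(t − t̄)² × (t_last − t_first).

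- Hospital-only, visit number 0 to 6: 0.5d/28 × 6 = +0.11d.
- Hospital-only, calendar days −30, 0, 2, 7, 14, 46, 107: −30.14d/11,668.9 × 137 = −0.35d.
- Hospital-only, baseline at day −60 and later visits at 19, 51 and 112: −19.79d/16,707.4 × 172 = −0.20d.
- Persisting, the same two sets of calendar days: 0.95d and 1.09d.

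The days are assumed. The plan does not state how time is coded, and for a hospital-only benefit the coding alone changes the sign.

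**Sidak level,** 1 − 0.95^(1/k), assuming independence: k = 4 gives 0.0127, k = 5 gives 0.0102 and k = 6 gives 0.0085.

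**The case against.** The strongest reply is that the plan is clearer than it looks.

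- **Scale.** A reader might infer that no fatigue scale is identified. The documents do not support that. The Aim 2 text equates the primary outcome with cancer-related fatigue, and Hypothesis 1a attaches FACIT-Fatigue alone to it. What stands is that this choice does not reach section 5d or Data Analysis.
- **Testing rule.** Only Data Analysis says how to test. An analyst who follows it would adjust depression, sleep, rhythms and quality of life. This stands: section 5d supplies conflicting labels, not a competing test procedure.
- **Inflated error.** A reader might infer a false-positive rate of about 10% (assumed correlation 0.8) to 14% (independence) from three fatigue scales each tested at 5%. That needs a rule that a positive result on any scale counts, and the documents state no such rule.
- **Model term.** The mixed-model framework is announced for Aims 1 and 2 together, and the Aim 2 text predicts that the interaction on fatigue will weaken when mediators enter. The interaction is thus signalled. It is still absent from the listed Aim 1 effects, and no contrast is named.
- **Wrong sign.** A reader might infer that a linear interaction would point the wrong way for a hospital-only benefit. That holds under the calendar-day coding assumed here, but not with visit number.
- **Inpatient measure.** The line scale replaces FACIT-Fatigue for daily ratings only. The documents do not say that FACIT-Fatigue is dropped at the scheduled inpatient assessments.
- **Purpose.** This is a feasibility study that seeks effect sizes. That lowers the stakes, but it makes a defined effect size more useful, not less.

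**Conclusion.** The contradiction between the two sections is certain from the text. So is the absence of an Aim 1 contrast and of a group-by-time term among the listed effects. The effect on the estimate is illustrative: the literal group effect recovers 0.64d of a persisting benefit and 0.36d of a hospital-only one. These figures rest on the assumed patterns and on FACIT-Fatigue at all seven assessments. The size and, for a hospital-only benefit, the sign of a linear interaction depend on a time coding that the plan leaves open.

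The point should be fixed, but it does not undermine the study. The harm is confined to the Aim 1 significance claim and to the effect size passed to the larger study.

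**What to change.** 1. Make section 5d match Data Analysis, with FACIT-Fatigue as the one primary outcome. Put the other fatigue scales, depression, sleep, rhythms and quality of life in the Sidak-adjusted secondary family in both places, and reword the remark that calls sleep a main outcome.
2. Give melatonin and the inflammatory markers the same label in both sections.
3. Add group-by-time to the Aim 1 fixed effects.
4. Pre-specify one between-group contrast in change from baseline during hospitalization. An example is engraftment day 3, with assessments entered as categories so that the result does not depend on time coding. Say which baseline is used when a second one exists. Make the one- and three-month contrasts secondary.
5. Confirm that FACIT-Fatigue is given at the assessment chosen.
6. Leave the light-exposure and satisfaction measures tied to Aim 3 as they are.

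The cost is wording in section 5d and Data Analysis. Fewer outcomes can be called primary. With six secondary measures (line scale, MFI, PSQI, CES-D, SF-36, actigraphy) the Sidak level is about 0.0085, against 0.010 to 0.013 for the four or five already covered by Data Analysis. An adjustment that uses the correlation would be somewhat less strict. Whether the stated power carries over to the chosen contrast cannot be confirmed from the documents, so the Power paragraph should say which scale and term it refers to.
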